14.3 Health Economics Evaluation

A switch from parenteral to oral antibiotics has the potential to reduce healthcare costs by reducing the observation time, facilitating an earlier discharge from hospital. A cost-consequence analysis will evaluate the impact of early discharge with oral antibiotics on healthcare resource use, costs and selected outcomes over a 28-day time horizon. The base-case analysis will be from a health service and personal social service perspective. Resource use data will be measured from randomisation until 28 days and will include length of stay, setting type (e.g. emergency assessment unit, ward, ambulatory care, HDU/ICU), readmissions to ED, outpatient visits and contacts with primary care. Data will be collected using the case report forms, medical records and a parent/guardian completed questionnaire. Costs will be calculated by attaching appropriate unit costs from publicly available sources (e.g. NHS Reference Costs) or hospital finance departments. We anticipate that 28 days will be sufficient to capture any readmissions. HRQoL of the participants will be measured within 24 hours of randomisation, 7 and 28 days using PedsQL Infant Scales 1-12 month Version (Acute) completed by the parent/guardian [32]. The PedsQL Family Impact Module (Acute) [34] will be used to measure the impact of the participants' health condition on the parents/guardians at 7 days. Discounting of costs and outcomes will not be required due to the short timeframe. Current guidelines for conducting [35-37] and reporting [38] economic evaluations will be followed where appropriate. Descriptive statistics (means, 95% confidence intervals) will be used to summarise (by treatment arm); health service use during primary hospital admission and after discharge until 28 days; associated costs; PedsQL Infant Scales and PedsQL Family Impact scores.

Sensitivity analyses will be conducted to explore the impact on the results of the costs-consequence analysis to variations in key assumptions. These will include an analysis from a broader societal perspective encompassing out-of-pocket costs borne by the parent/guardian (specifically due to inability to work/perform usual activities), and the impact of multiply imputing missing health economic data using chained equations and predictive mean matching. A health economic analysis plan will be written prior to analysis of these data.

14.4 Additional Analysis

Exploratory analyses for the primary outcome will be reported using interaction tests (treatment group by subgroup) and 99% confidence intervals for the following subgroups:

- I. Age (29-60 days, 61-90 days)
- II. Site
- III. Sex
- IV. Antibiotics pre randomisation
- V. Confirmed UTI*

14.5 Missing Data

Every effort will be made to minimise missing baseline and outcome data in this trial. The level and pattern of the missing data in the baseline variables and outcomes will be established by forming appropriate tables and the likely causes of any missing data will be investigated. This information will be used to determine whether the level and type of missing data has the potential to introduce bias into the analysis results for the proposed statistical methods, or substantially reduce the precision of estimates related to treatment effects. If necessary, these issues will be dealt with using multiple imputation or Bayesian methods for missing data as appropriate.

*Urinary Tract Infection (UTI) is defined as greater than 100,000 CFU/ml of a single, non-contaminant, organism from a single clean urine (clean catch, suprapubic aspiration, urethral catheter specimen) or greater than 100,000 CFU/ml of the same single organism from two non-clean urines (pads, bags, cotton wool).

15 STUDY WITHIN A TRIAL: Impact on recruitment by using an infographic in addition to the participant information sheet

15.1 Objectives

1. A cluster randomised study within a trial (SWAT) will be embedded within the EASY study to assess the impact on recruitment of using a simple specially developed information graphic (infographic) in addition to the standard PIS to explain the two treatment arms of the EASY Study to parents/guardians of eligible participants.
2. To explore satisfaction with and understanding of the EASY study consent process.

15.2 Background

Recruitment and retention to trials within a paediatric emergency setting is challenging as there is very little or no time for parents/guardians to consider research information and make an informed decision about their baby's involvement in a study. Parents can be distressed and understandably focused on their baby, often prioritising verbal information provided by clinicians over written study information. However, brief verbal information provision by practitioners in the emergency setting has been associated with poor parental understanding and poor recall of any aspect of the study presented [39]. Practitioner views and preferences may influence how they present the study, or be misunderstood by parents, which may impact upon trial recruitment and retention [40, 41].

We will explore ways to improve this in the EASY study, including assessing the effect of an infographic and collecting information on the consent process. Guidance on how to use the infographic will be provided during the site initiation visit (SIV). The infographic is a simple, brief representation of the information provided in the standard PIS about the two treatments and was developed with input from the PPIE group. The intention is to prompt a more structured conversation between the consenting clinician and the parent/guardian of the eligible child about the EASY study and how the randomisation will influence their child's care pathway.

After being provided with the PIS (and infographic if in the SWAT intervention arm) staff will ask each parent/guardian to complete a brief questionnaire within 48 hours post-screening. Staff will be asked to write the participants screening number at the top of the questionnaire. This will include parents who have been approached and declined their child's involvement in the trial. The questionnaire will aim to explore satisfaction with and understanding of the EASY study consent process, factors that may have informed decisions to decline participation in the EASY study and quality of decision making (measured using the validated SURE scale [42]). The questionnaire will be placed in a stamped self-addressed envelope and returned by post to the NICTU.

15.3 Intervention and Comparator (SWAT Objective 1)

EASY study sites allocated to the SWAT intervention arm will provide parents/guardians with an infographic in addition to the standard PIS during the consent process. Sites allocated to the control arm will use the standard PIS.

15.4 Participants

Parents/guardians of participants who are approached to participate in the EASY study.

15.5 Randomisation

The randomisation process will be separate from the main trial randomisation. Sites will be randomised (1:1 using mixed block sizes) to either the SWAT intervention or the SWAT control arm. The EASY study statistician will generate the randomisation sequence using NQuery Advisor.

15.6 Consent

Separate consent will not be required for Objective 1 (standard PIS versus standard PIS and infographic). For Objective 2 (questionnaire), consent will be implied by its completion and return, as it can be completed by all parents/guardians approached about the EASY study and not just those who consented for their child to participate.

15.7 Outcome Measures

Primary: Recruitment rates

Secondary:

- Immediate post-randomisation withdrawal rate (measured up to first dose of antibiotic post-randomisation)
- Retention rate at 28 days post-randomisation
- Cost per participant recruited and participant retained; calculated as the incremental cost of embedding the SWAT divided by the incremental number of participants recruited and the number of participants retained at 28 days.
- Satisfaction with and understanding of the consent process.
- Quality of parental decision making.

15.8 Analysis

Descriptive statistics will be used to summarise the outcomes by SWAT arm (where appropriate) including number (%), means (95% confidence intervals). A separate SWAT analysis plan will be written prior to final analysis of the data.

The SWAT is registered on the SWAT repository: SWAT225 [name], [name], [name], [name] (2022 SEP 1 2328).pdf (qub.ac.uk)

16 PHARMACOVIGILANCE

16.1 Definition of Adverse Events

The European Clinical Trials Directive 2001/20/EC and applicable clinical trial regulations set out the legal requirements for adverse event recording, management and reporting of clinical trials.

The MHRA Good Clinical Practice Guide 2012 provides the definitions given in Table 7.

Table 7: Terms and Definitions for Adverse Events

Term	Definition
Adverse Event (AE)	Any untoward medical occurrence in a participant to whom a medicinal product has been administered, including occurrences which are not necessarily caused by or related to that product.
Adverse Reaction (AR)	Any untoward and unintended response in a participant to an investigational medicinal product, which is related to any dose administered to that participant.
Suspected unexpected Serious Adverse Reaction (SUSAR)	A serious adverse reaction the nature and severity of which is not consistent with the information about the medicinal product in question set out: 
• in the case of a product with a marketing authorisation, in the Summary of Product Characteristics (SmPC) for that product• in the case of any other investigational medicinal product, in the Investigator's Brochure (IB) relating to the trial in question.
Serious Adverse Event (SAE), Serious Adverse Reaction (SAR) or Unexpected Serious Adverse Reaction	Respectively, any adverse event, adverse reaction or unexpected adverse reaction that: 
• results in death• is life-threatening• requires hospitalisation or prolongation of existing hospitalisation*• results in persistent or significant disability or incapacity• consists of a congenital anomaly or birth defect 
'Important medical events' may also be considered serious if they jeopardise the subject or require an intervention to prevent one of the above consequences.
 
The term 'life-threatening' in the definition of 'serious' refers to an event in which the patient was at risk of death at the time of the event; it does not refer to an event which hypothetically might have caused death if it were more severe.

*Hospitalisation is defined as an inpatient admission regardless of length of stay, even if the hospitalisation is a precautionary measure for continued observation. Hospitalisations for a pre-existing condition, including elective procedures that have not worsened, do not constitute an SAE.

16.2 Adverse Event Reporting

The AE reporting period for the trial begins upon consent and ends at day 28 (the last follow up assessment).

The PI or designee should record all directly observed AEs and all AEs spontaneously reported by the parent/guardian. In addition, the parent/guardian will be asked about AEs as part of the follow up assessments to be completed.

This paediatric population may experience a range of AEs such as common cold or other common childhood illnesses. Symptoms that are due to an alternative emergent condition (e.g. upper respiratory tract infection or other viral illness) should not be reported as an AE, unless the event is considered by the PI or designee to be associated with the study drug or unexpectedly severe or frequent.

Symptoms known to be associated with UTI (fever, vomiting, and interference with normal activity) will be captured as part of the follow up assessments and should not be reported as an AE. Events that are collected as outcomes for the EASY study do not need to be reported as AEs, including treatment failure, deterioration, hospital readmission and fever.

Laboratory confirmed invasive bacterial infections (IBI) including bacterial meningitis and symptomatic bacteraemia should be reported as AEs. Complications of peripheral venous access such as extravasation injury, tissue lines and line infections should be reported as AEs.

All other events should be reported, including new onset of vomiting, diarrhoea, rashes or oral thrush (or a change in severity or frequency of these) which are common side effects of parenteral and oral antibiotics. See section 16.7 for the recording and reporting of adverse events and serious adverse events.

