8.2.4 Blinding

This study will be a randomised, open label, unblinded trial. Parents/guardians, those who provide health care to the participants, and outcome assessors, will not be blinded to the allocated intervention in this trial. This reflects the pragmatic design focused on clinical effectiveness; it also permits realistic evaluation of the effect of the intervention on hospital admission to take account of admission for reasons other than parenteral antibiotic administration.

The trial statistician, who has no role in decision-making with regards the conduct of the trial, will be unblinded and this will also facilitate linkage with the DMEC. The remainder of the trial team will also be unblinded for the purposes of managing data collection, reviewing cases to assess protocol deviations, and to undertake pharmacovigilance duties.

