10.2 Secondary Outcomes

1. Treatment failure (i.e. additional parenteral antibiotics) assessed at day 28
2. Escalation in care defined as, escalation in the level of care (i.e. admission from home, admission to intensive care or a high dependency unit) OR change in antibiotic therapy OR death due to poor response. Assessed at 7 and 28 days.
3. Time to defervescence
4. Time to normal feeding (as reported by parent/guardian)
5. Time to normal activity (as reported by parent/guardian)
6. Length of stay
7. Antibiotic-associated adverse events (including diarrhoea and allergic reaction)
8. Antibiotic adherence (full course taken or no more than two missed doses)
9. Paediatric quality of life (measured using PedsQL acute infant version) within 24 hours of randomisation, day 7 and day 28
10. Family impact (measured using PedsQL Family Impact Module acute version) at day 7
11. Health service use and costs

11 SCREENING, CONSENT and RECRUITMENT

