16.3 Assessment of Causality

The PI or designee should make an assessment of causality, i.e. the extent to which it is believed that the event may be related to the intervention (Table 8).

Table 8. Categories of causality for adverse events

Category	Definition
Definitely*	Temporal relationship of the onset, relative to administration of the product, is reasonable and there is no other cause to explain the event, or a re-challenge (if feasible) is positive.
Probably*	Temporal relationship of the onset of the event, relative to the administration of the product, is reasonable and the event is more likely explained by the product than any other cause.
Possibly*	Temporal relationship of the onset of the event, relative to administration of the product, is reasonable but the event could have been due to another, equally likely cause.
Unlikely	Temporal relationship of the onset of the event, relative to administration of the product, is likely to have another cause which can by itself explain the occurrence of the event.
Not Related	Temporal relationship of the onset of the event, relative to administration of the product, is not reasonable or another cause can by itself explain the occurrence of the event.

* Where an event is assessed as possibly, probably or definitely related, the event is an AR.

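### Section 16.2 gives overlapping recording rules for diarrhoea, rash and vomiting, one of which turns on an unblinded causality opinion, and these events feed secondary outcome 7

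*Protocol*

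**What the plan says.** Secondary outcome 7 (Protocol 10.2) is "Antibiotic-associated adverse events (including diarrhoea and allergic reaction"). The trial is open label: under 8.2.4, "those who provide health care to the participants, and outcome assessors, will not be blinded to the allocated intervention".

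Four statements in section 16.2 bear on what is entered as an adverse event (AE):

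- General rule: "The PI or designee should record all directly observed AEs and all AEs spontaneously reported by the parent/guardian".
- Emergent-illness exemption: this covers "Symptoms that are due to an alternative emergent condition (e.g. upper respiratory tract infection or other viral illness"). The instruction to sites is that such symptoms "should not be reported as an AE, unless the event is considered by the PI or designee to be associated with the study drug". A second exception covers events that are unexpectedly severe or frequent.
- UTI-symptom and outcome exemptions: fever, vomiting and interference with normal activity are left to the follow-up assessments. Events collected as trial outcomes need not be reported as AEs.
- Closing rule: "All other events should be reported, including new onset of vomiting, diarrhoea, rashes or oral thrush (or a change in severity or frequency of these"). The reason given is that these are common side effects of both kinds of antibiotic.

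Table 7 in section 16.1 defines an AE without regard to cause, "including occurrences which are not necessarily caused by or related to that product". Causality is then handled in 16.3: "The PI or designee should make an assessment of causality", on a five-level scale that includes *Unlikely* and *Not Related*.

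**The concern.** In an infant who also has a viral illness, new loose stools or a rash can be put down to the virus or to the antibiotic. If the exemption governs, the decision to enter the event is itself a causality judgement, made by someone who knows the allocation and before the 16.3 grading takes place. If the closing rule governs, the event is entered and graded like any other. Sites may choose differently, and one investigator may choose differently by arm.

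At stake is the between-arm comparison of outcome 7. It could reflect attribution habits as well as incidence. An analysis plan cannot settle this later, because it is an instruction about which data are collected.

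**Working it through.** **1. The rules side by side.**

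| Symptom | Text pointing to not reporting | Text pointing to reporting |
|---|---|---|
| Diarrhoea or rash with a concurrent viral illness | Emergent-illness exemption, unless judged drug-associated or unexpectedly severe or frequent | Closing rule names both |
| Vomiting | Listed as a UTI symptom; also the emergent-illness exemption | Closing rule, if new or changed |
| Any antibiotic-associated AE | Events collected as outcomes need not be reported, and outcome 7 is an outcome | General rule and closing rule |

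No sentence sets an order of precedence. The phrase introducing the closing rule may mean whatever is left after the exemptions, or the list of named symptoms may override them. Both readings are open.

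**2. Could an unreported event be recovered?** Table 6 has a symptoms row, separate from the AE row, at baseline, within 24 hours, at 36–48 hours, at day 7 and at day 28. It also has antibiotic administration including tolerability at each post-randomisation time point. The only symptoms that 16.2 says follow-up captures in place of AE reporting are fever, vomiting and interference with normal activity. The protocol does not say whether the symptom record lists diarrhoea or rash. Recovery is therefore possible but not assured.

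**3. The plan's own figure, for context.** Section 14.1 uses a failure rate of 0.5%, a margin of 2%, 90% power and a one-sided 97.5% interval. Per arm, (1.96 + 1.2816)² × 2 × 0.005 × 0.995 / 0.02² = 261.4, so 262, or 524 in total, which matches. With 10% loss, 262 / 0.9 = 291.1, so 292 per arm and 584 in total, which also matches. None of this depends on outcome 7.

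**4. Illustration of size.** Assumptions, none of them in the protocol:

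- 262 infants per arm are analysed.
- The true rate *p* of diarrhoea or rash is the same in both arms.
- A share of events is dropped as viral: 20% in the oral arm and 40% in the parenteral arm.

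The recorded rates are *a* = 0.8*p* and *b* = 0.6*p*. The chance of a significant two-sided 5% test is approximately Φ((|a − b| − 1.96 × SE₀) / SE₁), where SE₀ is the pooled and SE₁ the unpooled standard error.

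For *p* = 20%: *a* = 16% and *b* = 12%; SE₁ = √((0.16 × 0.84 + 0.12 × 0.88) / 262) = 0.0303; SE₀ = √(2 × 0.14 × 0.86 / 262) = 0.0303; Φ((0.04 − 0.0594) / 0.0303) = Φ(−0.64) ≈ 26%.

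| True rate, both arms | Recorded, oral | Recorded, parenteral | Spurious difference | Significant test |
|---|---|---|---|---|
| 5% | 4% | 3% | 1 point | 9% |
| 10% | 8% | 6% | 2 points | 14% |
| 20% | 16% | 12% | 4 points | 26% |
| 30% | 24% | 18% | 6 points | 39% |

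Swapping the two shares reverses the sign and leaves the percentages unchanged. If 30% is dropped in each arm there is no spurious difference, only lower recorded rates. A wider gap (20% against 50% dropped) gives about 28%, 54% and 75% at true rates of 10%, 20% and 30%. The result follows the assumed gap, and the protocol gives no information about that gap.

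**The case against.** The strongest reply is that 16.2 already answers the question. Its closing rule names diarrhoea and rashes because they are antibiotic side effects, and a specific instruction would naturally prevail over a general exemption aimed at colds and common childhood illness. That reading is reasonable. A reader might infer from the exemption alone that diarrhoea or rash judged viral will go unreported; the text does not establish that. But it does not exclude it either, and sites need one rule.

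The exemption is also narrower than it first appears. It requires another emergent condition, and it lifts for unexpectedly severe or frequent events. Table 8 classes an event with an equally likely alternative cause as *Possibly* related, hence an adverse reaction. If that standard is used for drug association, many ambiguous cases would be reported. Section 16.2 does not say that it is. Similarly, the examples given for the outcome exemption (treatment failure, deterioration, readmission, fever) suggest that outcome 7 was not its target, but the wording does not exclude it.

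A reader might also infer that unreported events are lost for good. The separate symptom and tolerability records in Table 6 do not support that; recovery is uncertain, not impossible.

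On mechanism, the contrast between home and ward should not be pressed. Section 12.1 does not tie discharge to oral allocation, parenteral treatment is required only until culture results (typically 36 to 48 hours), and the day 7 and day 28 assessments are by telephone in both arms. Any difference in setting is likely to be concentrated in the first days. What stands is that attribution is made with knowledge of the arm.

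Finally, outcome 7 is by its name an attributed outcome. Replacing it with an all-cause count is a debatable trade-off, since background viral events add noise, and the protocol is not wrong to keep attribution in it.

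**Conclusion.** The point holds as an unresolved overlap in a data-collection rule. Section 16.2 points both ways for diarrhoea and rash during a concurrent illness, for vomiting, and, read literally, for any event that counts towards outcome 7. One of the paths makes entry depend on an allocation-aware opinion ahead of the 16.3 grading, although Table 8 already provides for events judged unrelated.

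The direction and size of any bias are unknown. The 9% to 39% range assumes 262 analysed per arm, equal true rates of 5% to 30%, and 20% against 40% dropped. It shows what unequal filtering could do, not what it will do.

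The effect is confined to a secondary safety outcome. The primary outcome and the sample size are untouched. The change is worth making because it is cheap and because data never entered cannot be dealt with in the analysis plan.

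**What to change.** State in 16.2 that new or worsened diarrhoea, vomiting, rash, oral thrush and allergic reaction are recorded as AEs in both arms to day 28 whatever the suspected cause, and that this overrides the emergent-illness, UTI-symptom and collected-as-outcome exemptions. Causality is then graded under 16.3 as for any other AE. Other common childhood illnesses can stay exempt as now.

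Keep outcome 7 as attributed events. Alongside it, report all recorded events of these types by arm, so that a reader can see whether attribution differed between arms.

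The cost is a short addition to 16.2, one extra table, and some additional AE entries for symptoms that are probably viral.

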12.1 Participant Assessments

The frequency of assessments and follow up are detailed in the schedule of assessments (Table 6). The schedule defines the timing of assessments (with windows) necessary for data collection. Participants should be followed until the final follow-up assessment at day 28, even if antibiotics have been discontinued.

The decision to discharge a participant home is not mandated by the allocation to the oral antibiotic treatment group. The local clinical team should determine when the participant should be discharged and have agreed that it is an appropriate management strategy.

Table 6: Schedule of Assessments

Day/Timepoint	Screening (Day 0)	Baseline (Day 0)	Within 24* Hours of Randomisation	36 – 48* Hours After Randomisation	Follow Up Day 7# (+/- 1 day)	Follow Up Day 28# (+/- 3 days)
At Hospital/Remote	Hospital	Hospital	Hospital/Remote	Hospital/Remote	Remote	Remote
Point of Care Dipstick Urinalysis	x					
Urine sample sent for microscopy and culture	x					
Eligibility	x					
Consent (Trial)		x				
Admission Details		x				
Demographics		x				
Medical History		x				
Symptoms		x	x	x	x	x
Physical Examination		x				
Full Blood Count (including CRP, Creatinine, Electrolytes)		x				
Medications		x	x	x	x	x
Hospital Resource Use			x	x	x	x
Antibiotic Administration (pre randomisation)		x				
Randomisation		x				
Antibiotic Administration (post randomisation) Including Adherence/Tolerability			x	x	x	x
Urine Culture Results			x	x		
Escalation in the level of care/Readmission			x	x	x	x
Adverse Events/ Serious Adverse Events		x	x	x	x	x
[§] PedsQL Infant (completed by parent/guardian)			x		x	x
[§] PedsQL Family Impact (completed by parent/guardian)					x	
SWAT Questionnaire on Consent (completed by parent/guardian)				x		
Health Resource Use and Activities Questionnaire (administered by site staff via telephone)						x

*Assessments will be face-to-face (hospital) or may be by telephone (remote) for participants who have been discharged. Within 24 hours, the parent/guardian should complete the PedsQL Infant Questionnaire. Within 36-48 hours, site staff should remind the parent/guardian to complete the SWAT Questionnaire.

#Assessments will be by telephone (remote) for both cohorts.

At day 7, site staff should remind the parent/guardian to complete the PedsQL Family Impact Questionnaire.

At day 7 and day 28, site staff should remind the parent/guardian to complete the PedsQL Infant Questionnaire.

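### Section 16.2 gives two overlapping rules for vomiting that starts or worsens after consent, so sites may differ on whether it is an adverse event

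*Protocol*

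**What the plan says.** Protocol 16.2 (Adverse Event Reporting) sets the reporting window: "The AE reporting period for the trial begins upon consent and ends at day 28 (the last follow up assessment"). Within it, two instructions bear on vomiting.

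- **Exemption.** "Symptoms known to be associated with UTI (fever, vomiting, and interference with normal activity) will be captured as part of the follow up assessments". The sentence goes on to say that these symptoms are not to be reported as AEs.
- **Requirement.** "All other events should be reported, including new onset of vomiting, diarrhoea, rashes or oral thrush (or a change in severity or frequency of these"). The reason given is "which are common side effects of parenteral and oral antibiotics".

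Secondary outcome 7 in section 10.2 reads "Antibiotic-associated adverse events (including diarrhoea and allergic reaction"). Vomiting is not named there, but the list is not closed.

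Table 6 (section 12.1) has a Symptoms row at baseline, within 24 hours, at 36–48 hours, day 7 and day 28. It has a separate row for AEs and SAEs, and another headed "Antibiotic Administration (post randomisation) Including Adherence/Tolerability" at each contact after randomisation.

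**The concern.** Every participant enters with suspected UTI (7.3.1), and section 4.1 lists vomiting among the non-specific features of UTI in young infants. Section 16.2 also calls it a common side effect of the trial drugs. When an infant starts vomiting after consent, site staff often cannot tell which of the two is responsible. The exemption points to the symptom record only, and the requirement points to the AE form.

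What is at stake is mainly the assessment attached to the event. The protocol prescribes causality (16.3), severity (16.4) and expectedness (16.6) assessment only within AE reporting. If a site treats the event as an exempt UTI symptom, nobody is asked to make those judgements, and a later analysis cannot recreate them. Parents, clinicians and outcome assessors all know the allocation (8.2.4), so an unclear rule leaves the classification to people who know the arm.

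**Working it through.** The protocol has no figure to reproduce here: it gives no expected rate of vomiting or of antibiotic-associated AEs. The check sets the two rules side by side.

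**1. Cases under each rule**

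| Event | Exemption | Requirement | Conflict? |
|---|---|---|---|
| Vomiting present at baseline, unchanged | Not an AE | Not triggered (neither new nor changed) | No |
| Vomiting new after consent | Not an AE, if seen as a UTI symptom | AE | Yes |
| Baseline vomiting that worsens in severity or frequency | Not an AE, if seen as a UTI symptom | AE | Yes |
| Diarrhoea, rash, oral thrush | Not listed | AE if new or changed | No |

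The overlap is confined to vomiting that starts or worsens after consent.

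**2. Does the text say which rule prevails?**

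- The exemption has no baseline limit. It speaks of symptoms recorded at follow-up, which is when new vomiting would appear.
- The paragraph before it exempts symptoms of other emergent illnesses but makes an exception where the investigator suspects the study drug, or where the event is unexpectedly severe or frequent. The UTI-symptom exemption has no such exception.
- The requirement opens by referring to all other events, which literally means those not already excluded. Vomiting had just been excluded by name.
- Against this, the requirement is the more specific of the two: it names new-onset vomiting expressly.

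The wording supports either reading.

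**3. What is recorded under each reading**

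Occurrence is in the Symptoms record either way. Causality, severity and expectedness are assessed only if an AE form is raised. Table 8 treats an event with plausible timing and an equally likely alternative cause as possibly related, and therefore as an adverse reaction. Vomiting that could be due to UTI or to the antibiotic fits that category, and the exemption can remove it before the judgement is made.

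**4. What this does to an arm comparison**

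Let *p*O and *p*P be the true risks of new or worsened vomiting in the oral and parenteral arms, and *f* the share of such events reported as AEs.

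- If readings differ only between sites, stratification by site (8.2.1) makes *f* about equal in both arms. This assumes that a site's reading is unrelated to its vomiting rates. The recorded difference is then *f* × (*p*O − *p*P), with 0 ≤ *f* ≤ 1. The difference shrinks, its sign does not change, and for *f* above 0 the ratio between arms is unchanged.
- If unblinded staff classify differently by arm, the recorded difference is *f*O × *p*O − *f*P × *p*P. This can move either way.

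The protocol supplies none of *f*, *p*O or *p*P. For scale only: at an assumed 5–20% in one arm of 584 / 2 = 292 infants, the events open to either classification would number 292 × 0.05 = 14.6 (about 15) to 292 × 0.20 = 58.4 (about 58). These are not estimates of events lost.

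**The case against.** The strongest reply is that the two sentences form a general rule and a specific exception. Vomiting from the presenting illness is a symptom, and new or changed vomiting is an AE. Table 6 takes symptoms at baseline, which gives the reference for deciding what is new or changed. This is the natural reading and probably what was meant. It still has to be supplied by the reader, because the exemption carries no limit.

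A second reply is that no data are lost, since symptoms are recorded at every contact. That is right for occurrence, but not for the assessments in 16.3, 16.4 and 16.6.

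Three stronger inferences are tempting, and the documents do not support them.

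- **That 16.2 flatly forbids reporting vomiting.** It exempts vomiting as a symptom associated with UTI, and the same section then names new-onset vomiting as reportable.
- **That outcome 7 is miscounted.** That outcome names diarrhoea and allergic reaction. Vomiting may enter through the open list, but this is an inference, and the derivation may properly sit in the analysis plan.
- **That the oral arm will look better tolerated than it is.** Section 16.2 attributes these side effects to both routes. The dose-repeat rule in 9.2 says nothing about relative rates. Differing site readings would shrink a difference rather than favour one arm. A distortion in favour of oral treatment would need an oral excess or arm-specific judgement that the protocol does not show.

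**Conclusion.** The point holds as an ambiguity in AE classification. For vomiting that starts or worsens after consent, section 16.2 supports both reporting and not reporting, and a sensible reconciliation is available but not written down. AE counts may therefore be inconsistent between sites, and some possibly drug-related events may never receive a causality, severity or expectedness judgement. Outcome 7 is affected only if vomiting is counted in it.

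The size and direction of any effect on the arm comparison cannot be derived from the protocol. The treatment-failure outcome, the non-inferiority conclusion and the sample size do not depend on this. The conclusion rests on the wording of 16.2 and on AE assessment being the only place where the protocol prescribes those three judgements. It is worth correcting because the correction is small and changes what sites record.

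**What to change.** Reconcile the two sentences in 16.2:

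1. Limit the UTI-symptom exemption to symptoms present at baseline and not worse since. Vomiting that is new, or changed in severity or frequency, from consent onwards is then reported as an AE in both arms. Consent is the right starting point because the AE period opens there; counting from randomisation would leave out events between the two. Fever stays exempt under the separate sentence in 16.2 on events collected as outcomes.
2. State whether such vomiting counts towards secondary outcome 7. If it does, check it in the same way in both arms against the Symptoms record already in Table 6.

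The cost is one or two sentences and slightly more AE forms for sites. No new data collection is needed.
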